7.0 Statistical plan

7.1 Statistical Analysis

The primary comparison is between treatment assignment and organ-failure-free days at 28 days. Secondary analyses are the evaluation of adequacy of screening, enrollment, and study protocols.

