1.0 Abbreviations and Definitions

APACHE II = Acute Physiology and Chronic Health Evaluation, version 2
BIDMC = Beth Israel Deaconess Medical Center
CVP = Central venous pressure
ECMO = Extracorporeal Membrane Oxygenation
ER = Emergency Room
GVEC = Graded Volume Expansion Challenge
ICU = Intensive Care Unit
IMC = Intermountain Medical Center
ITT = Intention to Treat
LAR = Legally Authorized Representative
OFFD = Organ-Failure-Free Days at 28 days
P/F = PaO₂/FiO₂ ratio
SAE = Serious Adverse Event
ScvO₂ = Central venous oxygen saturation
SMC = Safety Monitoring Committee
SOFA = Sequential Organ Failure Assessment score
SUSAR = Serious and Unexpected Suspected Adverse Reaction

Definitions

Adverse Event: Any untoward medical occurrence associated with the use of a drug or study procedure, whether or not considered drug related. (cf. 21 CFR 312.32(a))

Adverse reaction: An adverse reaction means any adverse event caused by a drug. Adverse reactions are a subset of all suspected adverse reactions where there is a reason to conclude that the drug caused the event.

Intention to Treat (ITT): All eligible and consented patients who undergo esmolol infusion will be included in the ITT cohort for the purposes of analyzing the primary and secondary study outcomes.

Legally Authorized Representative: An individual, judicial, or other body authorized under applicable law to consent on behalf of a prospective patient to the patient's participation in the clinical study.

Life-threatening adverse event or life-threatening suspected adverse reaction: An adverse event or suspected adverse reaction is considered "life-threatening" if, in the view of the investigator, its occurrence places the patient or subject at immediate risk of death. It does not include an adverse event or suspected adverse reaction that, had it occurred in a more severe form, might have caused death. (cf. 21 CFR 312.32(a))

Organ-failure-free days: As of day 28, the number of calendar days on which the patient receives none of (a) vasopressor therapy, (b) mechanical ventilation, or (c) renal replacement therapy. If the patient dies on or before day 28, they have -1 organ-failure-free days.

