2.0 Study Summary

2.1 **Title:** Esmolol to Control Adrenergic Storm in Septic Shock (ECASSS) – ROLL-IN

2.2 **Objective:** To evaluate the adequacy and efficiency of study protocols for the main ECASSS study.

2.4 **Study design:** Prospective, single arm, feasibility (“roll-in”) study of esmolol infusion in septic shock.

1. **Inclusions.** We will include patients admitted to the ICU for sepsis who are within 48 hours of septic shock and ICU admission and are simultaneously tachycardic (heart rate >90/min) **and** on vasopressors for > 60 min. Patients must meet criteria at the time of enrollment.
2. **Final safety check.** After enrollment and before esmolol infusion, ScvO₂, transthoracic echocardiogram, evaluation of fluid responsiveness, and review of telemetry/EKGs will occur to assure that no exclusion criteria are present.
 - a. If no exclusion criteria are present, patients will start esmolol infusion
 - b. If patient is still fluid responsive but otherwise has no exclusions, fluid will be administered by explicit protocol until no longer fluid responsive, and then the patient will receive esmolol infusion. If tachycardia has resolved as a result of volume expansion, esmolol infusion will not occur until tachycardia and vasopressor administration co-occur. After esmolol infusion, volume expansion will be managed as part of the esmolol titration protocol.
 - c. Patients who fail the final safety check will NOT start esmolol infusion but will be followed for non-interventional aims (e.g., serial TTEs, vascular biomarkers) to understand better the natural history of cardiogenic shock superimposed on septic shock.
3. **Esmolol infusion**
 - a. Esmolol infusion, started without bolus, with slow upward titration to a maximum infusion rate is protocolized (see protocol in Appendix 1), with a target heart rate of 80-90/min.
 - b. Esmolol infusion will be stopped in the event that cardiogenic shock, excessive bradycardia, grade 2 or grade 3 heart block, or hypotension, or bronchospasm occur, as per protocol.
4. **Other care**
 - a. ICU patients are managed according to current Surviving Sepsis campaign guidelines as per usual practice.

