 - a. For the esmolol titration protocol, each hour (the closest value of heart rate to the hour) during the esmolol infusion will be determined to be “in range” or “out of range,” with 3bpm margin for compliance (i.e., heart rate 77 to 93bpm). The initiation and cessation of esmolol will also be included as a timepoint for evaluation of compliance. Protocol compliance is considered adequate where overall compliance on hourly checks is >80%.
 - b. For STOP events, protocol compliance is considered adequate at 100%.
 - i. 30min moving average of cardiac index below threshold
 - ii. 30min moving average of norepinephrine infusion rate above threshold
 - iii. Clinician determines that shock has substantially worsened on esmolol.

- c. For VOLUME EXPANSION events, protocol compliance is considered adequate at 90%.
- 4. Amount of research coordinator time spent on different tasks

2.8.1 Anticipated primary clinical outcome for main trial (this will also be recorded for ROLLIN): Organ-failure-free days at 28 days. An organ-failure-free day is defined as a calendar day on which the patient receives none of (a) vasopressor therapy, (b) mechanical ventilation, or (c) renal replacement therapy.

2.8.2 Anticipated secondary clinical outcomes for main trial (these will also be recorded for ROLLIN):

1. All-cause hospital mortality
2. All-cause 28-day and 90-day mortality
 - a. Mortality will be ascertained through telephone followup for patients who were discharged alive before 90 days.
3. Peak serum high-sensitivity troponin
 - a. Troponin will be measured on day 0 and day 1.
4. LV global longitudinal strain at 24 hours
5. Time to transition to quiescent vascular phenotype, as defined by serum Angpt-2 level < 1ng/ml.
6. ICU-free days to day 28
 - a. Patients who die before 28 days will be assigned -1 ICU-free days, using a methodology similar to that used for organ-failure-free days.
7. Cardiogenic shock/requirement for inotropes through day 14. This is a binary variable and is met when any of the following is present
 - a. Dobutamine or milrinone infusion at any dose, lasting > 60min
 - b. $CI \leq 2$ L/min/m² lasting > 30 min on NICOM
 - c. $ScvO_2 \leq 60\%$ on any measurement
8. Development of second or third degree heart block.

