3.2 Study Design

Prospective, single arm, feasibility (“ROLL-IN”) study of esmolol infusion in septic shock.

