3.3 Objective

To assess the adequacy of subject identification and enrollment procedures. To assess the adequacy and efficiency of study protocols. To evaluate the estimates of coordinator burden for screening and enrollment.

3.5.1 Non-clinical outcomes for ROLL-IN:

1. Proportion of eligible patients consented
2. Proportion of protocol compliance
3. Amount of research coordinator time spent on different tasks

3.5.2 Anticipated primary clinical outcome for main trial: Organ-failure-free days at 28 days. Defined as the number of calendar days on which the patient receives none of (a) vasopressor therapy, (b) mechanical ventilation, or (c) renal replacement therapy. (Patients who die before 28 days will be assigned -1 organ-failure-free days in order to avoid making death equivalent to prolonged organ dysfunction.) For example, a patient who died on day 12 would have -1 organ-failure-free days, while a patient who resolved all organ dysfunction on day 9 but died on day 30 would be categorized as having 19 organ-failure-free days.

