7.2 Sample size

This “roll-in” feasibility study will allow us to confirm the adequacy of compliance with management protocols, and the time intensity of study enrollment and CRF completion. These roll-in data will be used to allow rapid initiation of a much larger multi-center trial once funding is secured.

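### Section 7.1 makes a comparison by treatment assignment the primary analysis of a single-arm study, so it cannot be estimated, and it ranks the feasibility evaluations as secondary

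*Combined protocol and SAP*

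**What the plan says.** Section 7.1 is two sentences long. The first reads "The primary comparison is between treatment assignment and organ-failure-free days at 28 days"; the second reads "Secondary analyses are the evaluation of adequacy of screening, enrollment, and study protocols". No other part of the document names a primary analysis for the roll-in.

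The rest of the document describes a different study:

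- **Design (3.2, and likewise 2.4):** "Prospective, single arm, feasibility".
- **Objectives:** section 2.2 gives "To evaluate the adequacy and efficiency of study protocols for the main ECASSS study". Section 3.3 begins "To assess the adequacy of subject identification and enrollment procedures" and goes on to protocol adequacy and coordinator burden.
- **Outcomes:** 2.8 and 3.5.1 list the roll-in outcomes as non-clinical: consent, compliance and coordinator time. Section 2.8.1 introduces organ-failure-free days as "Anticipated primary clinical outcome for main trial (this will also be recorded for ROLLIN".
- **Sample size rationale (7.2):** the study "will allow us to confirm the adequacy of compliance with management protocols". The only other purposes given are the time demands of enrollment and form completion, and preparation for the larger trial.
- **Analysis cohort (1.0):** "All eligible and consented patients who undergo esmolol infusion will be included in the ITT cohort", and this cohort is to be used for the primary and secondary outcomes.

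**The concern.** A comparison by treatment assignment needs at least two assigned groups, and a single-arm study has one. If no comparator exists anywhere in the document, the stated primary analysis cannot be carried out.

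The second sentence of 7.1 adds to the problem. It places the evaluations that answer the study's own objectives below an analysis that cannot be done, and it does not point to the compliance thresholds set in 2.8. Whoever analyzes the study is left without a usable statement of which result decides whether the roll-in succeeded.

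There is also a risk in trying to follow 7.1 literally. The only contrast available among enrolled patients is infused versus not infused. Patients are left uninfused because of their clinical state, so that contrast would be confounded and could be misread as an effect of esmolol.

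**Working it through.** The plan gives no effect size, standard deviation, alpha or power for this comparison, so there is no figure of its own to reproduce. The check is whether the comparison can be estimated, and then whether anything in the document could rescue it.

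**1. Estimability.** The inputs are one arm (2.4, 3.2), a cohort of infused patients only (1.0), and up to 10 patients (2.7; section 4.0 says 10).

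- The comparison would be mean OFFD (assigned esmolol) − mean OFFD (assigned comparator), where OFFD is organ-failure-free days. Its variance is σ² × (1/n₁ + 1/n₀). With n₀ = 0, the second mean does not exist and 1/n₀ is undefined.
- Put as a regression, the model has an intercept and a treatment indicator. With all 10 patients coded 1, the two columns are identical. The design matrix has 2 columns and rank 1, so the treatment coefficient is not identifiable.
- Neither result depends on n₁. This is a structural problem and not one of low power.

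**2. Possible comparators in the document.**

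- *Enrolled patients who are not infused.* Under 2.4 (item 2), 5.1.1.1 and 5.1.1.2, patients who fail the final safety check do not start esmolol but are followed. Section 2.4 also defers infusion while tachycardia has resolved after volume expansion. In each case clinical findings decide, not assignment, and a patient who is never infused is outside the cohort in 1.0.
- *The parallel center (7.3).* This is described as a study under a similar protocol whose data will be shared to analyze experience at two centers. No control group and no comparator role is described.
- *Mention of randomization (10.1).* The adverse-event text refers to events after randomization, but no randomization procedure appears anywhere.
- *Mention of efficacy (9.2).* The justification for including vulnerable subjects refers to safety and efficacy but supplies no comparator.

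None of the four provides an assigned comparison group.

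**3. Ranking.** Sections 2.2, 3.3 and 7.2 give feasibility as the purpose, 2.8 and 3.5.1 list feasibility outcomes for the roll-in, and 2.8.1 and 3.5.2 assign organ-failure-free days to the main trial. Only 7.1 puts feasibility second. Section 2.8 already sets criteria for adequacy: 100% for the safety check, more than 80% for hourly heart-rate checks, 100% for STOP events and 90% for VOLUME EXPANSION events.

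**4. What the corrected analysis could show, for scale only.** The exact (Clopper-Pearson) 95% interval when all n patients are compliant has lower limit 0.025^(1/n) and upper limit 100%.

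- n = 10: 0.025^(1/10) = 0.692, so 69.2% to 100%.
- n = 6: 0.025^(1/6) = 0.541, so 54.1% to 100%. Six is the second safety-committee review point and serves only as an illustration of smaller enrollment.

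For a single-arm mean of organ-failure-free days, the 95% half-width is t₀.₉₇₅,₉ / √10 = 0.72 standard deviations at n = 10. The document gives no standard deviation, and the outcome is skewed (−1 for death), so this is approximate and stays in standard-deviation units.

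**The case against.** The strongest reply is that little turns on 7.1. No sample size, error rate, stopping rule or patient handling depends on it. Every other relevant section makes the feasibility purpose plain, and the sentence looks like main-trial wording carried over (an inference). All of that is fair, and it limits the harm to analysis and reporting. It does not make 7.1 usable: this is the only place that names a primary analysis, and what it names cannot be done.

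A second reply is that the thresholds are not really cut off from 7.1, because 7.1 speaks of adequacy and 2.8 defines adequate compliance. That stands in part. The criteria exist; what is missing is a cross-reference and the right rank.

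Third, section 7.3 is silent on arms at the other center, so one can say only that no control group is described, not that none exists. That is correct, but an undescribed group cannot be the assigned comparator in 7.1.

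Fourth, the exact intervals do not measure the defect, and 2.8 judges adequacy on observed percentages. This also stands: the intervals show only the precision available once the section is corrected. They assume one safety check per patient, which 2.8 does not state.

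Finally, a replacement for 7.1 should not lose the evaluation of screening that the section now includes. That is right, and the text proposed below names screening.

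**Conclusion.** The concern holds on both counts. The stated primary comparison has one level of treatment assignment and 0 assigned comparators, so it cannot be estimated however many patients are enrolled. The ranking in 7.1 reverses the purpose stated in 2.2, 3.3 and 7.2.

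The conclusion rests on the design, cohort and outcome definitions as written and on no numerical assumption. It does not mean that organ-failure-free days cannot be reported; a descriptive summary in one arm is possible, and only the comparison is not. The consequence is limited to analysis and reporting, but it concerns the primary analysis itself, so it should be corrected before any analysis is done.

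**What to change.** Replace section 7.1 with text along these lines:

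> The primary analyses are the feasibility outcomes in section 2.8. Screening is summarized from the screening log. The proportion of eligible patients who are consented (denominator: eligible patients) and the proportion of enrolled patients with a compliant final safety check (denominator: enrolled patients) are each reported with an exact 95% confidence interval; these two proportions are not restricted to the ITT cohort. Titration, STOP-event and VOLUME EXPANSION compliance are reported as observed overall proportions set against the section 2.8 thresholds, with per-patient summaries. Coordinator time is reported by task (median and range). Organ-failure-free days and the other clinical outcomes are secondary and descriptive, reported for infused patients and listed separately for enrolled patients who were not infused. No treatment-effect comparison is made, including infused versus not infused. The two-center description in section 7.3 is unaffected.

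The intervals, the per-patient summaries and the choice of median and range are suggestions. The essential changes are to remove the comparison, make feasibility primary with a link to 2.8, and keep organ-failure-free days descriptive. The reference to randomization in section 10.1 should be corrected at the same time.

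The cost is a few sentences in 7.1 and one phrase in 10.1, with no new data or patients. The only drawback is a slightly longer analysis section.

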7.2 Sample size

This “roll-in” feasibility study will allow us to confirm the adequacy of compliance with management protocols, and the time intensity of study enrollment and CRF completion. These roll-in data will be used to allow rapid initiation of a much larger multi-center trial once funding is secured.

7.3 Additional data

Investigators at the University of Chicago are performing a parallel study under similar protocol, overseen by the University of Chicago IRB and monitored by their own Safety Monitoring Committee. Data from the University of Chicago study will be shared with investigators at IMC to allow analysis of the experience at the two centers. All data transfers will be over-seen by applicable IRB approvals, consent documents, and data use/data sharing agreements and will not occur without appropriate agreements and

approvals in place. Data privacy and confidentiality for the University of Chicago data will comply with relevant regulations and safeguards.

8.0 Risk Assessment

8.1 Potential Risks

There are potential risks (as well as benefits) to study subjects. Selective β 1-blockade in septic shock has reasonable pilot data in favor of its safety; our observations about improved survival with relative bradycardia also suggest that interventions to induce relative bradycardia will be safe. The primary concerns about risk related to β 1-blockade in septic shock (based on theoretical considerations) are of decreased cardiac output, which is why we will titrate esmolol without bolus doses, starting at very low doses, and we will exclude patients with preexisting or intercurrent cardiogenic shock. After enrollment and before esmolol infusion, we will perform a final verification that cardiogenic shock is not present (using the NICOM™ measurements and initial research echocardiogram). Patients with preexisting conduction system disease may also be at risk for heart block or excessive bradycardia, so they are excluded from this study as well (this will also be verified before esmolol infusion, from the EKG monitors at the patient's bedside).

We have chosen esmolol because it is β 1-selective (thereby decreasing the hypothetical risk of pulmonary effects possible with non-selective β -blockade), because it is available as a continuous infusion (thereby limiting the risk of bolus-associated adverse effects) and because it has a very short half-life (allowing essentially immediate cessation of effect when the infusion is stopped). The theoretical side effects of esmolol infusion would all reverse within minutes of discontinuation of esmolol, and explicit rules will dictate discontinuation of esmolol infusion.

8.1.1 Alternative treatments

While some individual clinicians have advocated use of intravenous metoprolol, another β 1-blocker, the longer duration of action and the lack of availability as a continuous infusion led us not to recommend metoprolol for this trial. There is no evidence-based alternative treatment currently available for the adrenergic over-stimulation associated with septic shock. Since participation in this study is voluntary, all patients who choose not to enroll will receive the treatment consistent with the highest standard of care established at their institutions.

8.2 Risk abatement strategies

8.2.1 Cardiogenic shock. As indicated above, patients with preexisting cardiogenic shock are excluded from enrollment, and after enrollment a formal evaluation to exclude cardiogenic shock will be performed before esmolol infusion. The esmolol titration protocol incorporates continuous monitoring of cardiac output using the non-invasive NICOM™ device, and in the rare situation that cardiogenic shock should ensue, esmolol titration will be discontinued and appropriate supportive measures will be instituted. Our use of a no-bolus, slow upward titration protocol for the esmolol infusion is specifically designed to avoid this potential complication.

8.2.2 Excessive bradycardia and/or hypotension. As indicated above, patients with preexisting conduction system disease are excluded from enrollment, and a formal evaluation to exclude conduction system disease will be performed before esmolol infusion. In the event that hypotension or excessive bradycardia should ensue during esmolol infusion, esmolol will be discontinued and appropriate supportive measures will

be instituted. Our use of a no-bolus, slow upward titration protocol for the esmolol infusion is specifically designed to avoid this potential complication.

8.2.3 Hypersensitivity reaction. This is extremely rare. Patients with known hypersensitivity to esmolol or vehicle are excluded from the study. Should this occur, esmolol infusion will be stopped and appropriate treatment measures will be instituted. The short half-life of esmolol avoids concerns about treatment of anaphylaxis in patients on β -blockers, should anaphylaxis occur.

8.3 Protection against loss of privacy/breach of confidentiality

In order to protect a potential subject's privacy, study staff will only approach potential subjects (or LARs) in a private setting. Once consented, we will take multiple steps to protect the study subject from breach of confidentiality. The list linking the subject's name and medical record number will be kept behind the hospital firewall in a password-protected file. This file is only accessible through the hospital server to those individuals given password approval to access the file. Furthermore, the electronic database (REDCap) will be coded with a unique study identifier rather than with individually identifiable PHI (other than certain dates of service, as indicated above). The paper copy of CRFs will be stored in a locked cabinet at Intermountain Medical Center. The plasma sent to BIDMC for vascular biomarker assays will be managed according to standard practice for research samples, under an appropriately executed material transfer agreement.

8.4 Potential benefits

If esmolol proves efficacious, we anticipate a direct benefit to patients receiving esmolol infusion, specifically improvements in organ-failure-free days and/or survival.

